Immunogenicity will be assessed by screening for anti-drug antibodies (ADAs) at baseline and every 3 months during the first year and every 6 months thereafter. ADAs will be measured on blood samples collected at troughs (pre-dose). Testing will follow a tiered approach consisting of screening, confirmation, titration, and additional characterization of confirmed ADA positive samples.

STATISTICAL METHODS

Safety data will be listed by subject and summarized by cohort using frequencies or descriptive statistics. All subjects who receive at least one dose of somavaratan will be included in the safety analysis. Summaries of all adverse events (AEs), serious adverse events (SAEs), and incidence of Grade 3 or 4 adverse events will be classified according to severity and relationship to study drug.

No formal hypothesis testing is planned for this extension study.

For continuous variables, descriptive statistics will include the number of subjects, mean, standard deviation (SD), median, minimum, and maximum. For categorical variables, descriptive statistics will include the number and percentage of subjects in each category.

Summaries of subject disposition, demographics, disease characteristics, and exposure and response to dosing of study medication will be provided.

Somavaratan ADAs will be summarized descriptively.

AEs, PK, and PD will also be descriptively summarized by ADA subgroup (positive, negative) to assess potential effects of ADA positivity.

TABLE OF CONTENTS

APPROVAL/SIGNATURE PAGE: SPONSOR AND CONTRACT RESEARCH ORGANIZATION	2
SYNOPSIS: PROTOCOL 15VR8.....	3
LIST OF ABBREVIATIONS AND DEFINITIONS OF TERMS.....	15
1 INTRODUCTION	22
1.1.1 Adult Growth Hormone Deficiency.....	23
1.1.2 Pediatric Growth Hormone Deficiency	24
1.1.3 Summary of Clinical Experience	26
2 STUDY OBJECTIVES.....	28
2.1 Primary Objective.....	28
2.2 Secondary Objectives.....	28
3 INVESTIGATIONAL PLAN.....	29
3.1 Overall Study Design and Plan.....	29
3.2 Rationale for Study Design.....	31
3.3 Dose Selection	31
3.4 Study Duration and Dates.....	32
3.5 Safety Review and Stopping Rules.....	32
3.5.1 Stopping Rules.....	32
STUDY POPULATION SELECTION	33
3.6 Study Population.....	33
3.7 Inclusion Criteria:	33
3.8 Exclusion Criteria:	34
3.9 Subject Withdrawals and Replacements.....	35
4 STUDY TREATMENT(S).....	36
4.1 Description of Treatment(s).....	36
4.1.1 Somavaratan Treatment	36
4.2 Treatments Administered.....	36
4.3 Selection and Timing of Dose for Each Subject.....	37

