Despite dose adjustments (reductions), of the 29 subjects that completed 5 doses in the Phase 2 study at the time of this protocol amendment, IGF-I values 7 days after the last (fifth) dose were > 2.0 SDS in 16 subjects (55%) and > 3.0 SDS in 7 subjects (24%).

Based on these findings, it was determined that:

- A lower starting dose is needed
- The maintenance doses in rollover subjects seems to be too high, and a lower maintenance dose is needed
- The dose titration plan was not adequate to address the high IGF-I levels at Day 8 and a new titration plan based solely on IGF-I SDS 7 days after dosing is proposed
- The dosing frequency should be revised to twice-monthly to allow for adequate response during the dosing interval with reduced IGF-I excursions above 2.0 SDS
- Dosing initiation and titration should be made on a fixed (mg) basis and not be based upon-body weight adjusted (mg/kg) basis

Starting Dose

Evaluation of the doses resulting in Day 8 IGF-I above and below 2.0 SDS indicate that for adult subjects with GHD (except women receiving estrogens), 20 mg was the lowest dose that did not result in a response > 2.0 SDS in 90% of the subjects. For women receiving estrogens, a similar analysis was performed and the identified starting dose was 40 mg.

A fixed starting dose regardless of weight, age and gender is therefore planned for this study:

- 20 mg for all subjects other than women receiving oral estrogen
- 40 mg for women receiving oral estrogen

Dosing Frequency

Data from the ongoing analysis of the Phase 2 study have shown that the pre-dose (trough) IGF-I levels were similar to the baseline IGF-I levels (prior to any somavaratan exposure), suggesting that the duration of effect was less than one month. In addition, after the last (fifth) dose of somavaratan in the Phase 2 study, IGF-I levels at 21 days after dosing had already diminished to values not different than the pre-dose levels. Based on this analysis, the planned dosing frequency for this study is:

- Twice-Monthly

Continued Dosing in Rollover Subjects Presently Participating in This Study

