3.4 Study Duration and Dates

This study is a long-term evaluation of somavaratan administered twice-monthly. Subjects may continue on somavaratan treatment until the product is commercially available in their country or until the study is discontinued by the sponsor.

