8 PLANNED STATISTICAL METHODS

8.1 General Considerations

This section presents a brief summary of the planned statistical analyses. A statistical analysis plan that describes the details of the analyses to be conducted will be finalized prior to database lock and un-blinding.

All summaries will be presented by cohort.

Summary statistics will be provided for the variables described below as follows. For continuous variables, these statistics will include the number of subjects, mean, standard deviation (SD), median, minimum, and maximum. For categorical variables, these statistics will include the number and percentage of subjects in each category.

The last observation obtained prior to the first dose in the current study will be used as the Baseline value for calculating change from Baseline.

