8.2 Analysis Populations

8.2.1 *Safety Population*

The safety population will consist of all subjects who receive any amount of study drug.

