8.5 Safety

Safety analyses will be conducted on the safety population and will be summarized by cohort. Safety variables include AEs, clinical laboratory values, vital signs, and physical examination results.

AEs will be coded using MedDRA and will be summarized using the coded terms. Summaries of all treatment emergent adverse events (TEAEs), serious adverse events (SAEs) and Suspected, Unexpected Serious Adverse Reactions (SUSARs) will be presented. The incidence of CTCAE V.4.0 Grade 3 or 4 adverse events will be classified according to severity and relationship to study drug.

Observed and change from Baseline values for laboratory safety panels and vital signs will be summarized using descriptive statistics. Laboratory results will also be summarized and presented as shifts from Baseline.

No formal inferential analyses will be conducted for safety variables.

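### Adverse-event percentages in an open-ended study with staggered entry are not tied to time observed, so the primary safety summaries cannot separate risk from length of follow-up

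*Combined protocol and SAP*

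**What the plan says.** Section 2.1 makes safety during long-term treatment the primary objective. The synopsis (Statistical Methods) says: "Safety data will be listed by subject and summarized by cohort using frequencies or descriptive statistics". Section 8.1 sets the general rule: "For categorical variables, these statistics will include the number and percentage of subjects in each category". Section 8.5 adds "The incidence of CTCAE V.4.0 Grade 3 or 4 adverse events will be classified according to severity and relationship to study drug", with no denominator in time. The denominator is in Section 8.2.1: "The safety population will consist of all subjects who receive any amount of study drug".

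Follow-up is open-ended. Section 3.4 says: "Subjects may continue on somavaratan treatment until the product is commercially available in their country or until the study is discontinued by the sponsor". Entry is sequential (Section 4.4). The Version 2 rationale has a heading "Continued Dosing in Rollover Subjects Presently Participating in This Study", so some subjects were on treatment in this study before others had entered.

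Exposure does appear in the synopsis: "Summaries of subject disposition, demographics, disease characteristics, and exposure and response to dosing of study medication will be provided". Nothing in the supplied text connects that summary to AE incidence. The text has no rate per person-year, time-to-first-event summary, AE table by time interval or fixed AE window. The synopsis also plans AE summaries by ADA subgroup, without saying when a subject's status is fixed.

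**The concern.** An n (%) table counts a subject once, whether that subject was watched for three months or three years. When follow-up is unequal, the percentage depends on both the event rate and the observation time. It keeps rising as the study continues even if risk is constant.

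No formal inference is planned, so these descriptive figures are the primary result. Someone comparing one data cut with the next, one cohort with the other, or this study with another source could not tell more risk from more time. A separate exposure table does not repair this. Person-time to first event, for each event type, cannot be recovered from total exposure set beside a count.

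**Working it through.** The documents give no AE rate, follow-up distribution or expected event count, so there is no plan figure to reproduce. The inputs below are assumptions unless a section is named.

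**1. Crude percentage against time.** With a constant first-event hazard λ, the expected crude percentage at time t is 1 − exp(−λt).

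| Assumed λ (per person-year) | 0.5 y | 1 y | 2 y | 3 y |
|---|---|---|---|---|
| 0.05 | 2.5% | 4.9% | 9.5% | 13.9% |
| 0.10 | 4.9% | 9.5% | 18.1% | 25.9% |
| 0.30 | 13.9% | 25.9% | 45.1% | 59.3% |

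Within each row the risk per unit time is the same. First events per person-year at risk would estimate 5, 10 or 30 per 100 person-years in every column.

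**2. The reverse direction.** A crude 20% corresponds to −ln(0.8)/t. That is 22.3 first events per 100 person-years if everyone was followed for 1 year, and 0.2231/3, or 7.4, if everyone was followed for 3 years.

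**3. Precision of a rate.** At assumed exposures, exact Poisson 95% intervals per 100 person-years are:
- 12 first events in 125 person-years: 9.6 (5.0 to 16.8)
- 25 in 250: 10.0 (6.5 to 14.8)
- 50 in 500: 10.0 (7.4 to 13.2)

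**4. Why rollover and naive subjects need separating.** Sections 1.1.2 and 5.7.5 liken related AEs to those seen when rhGH is started. Suppose this means a higher early rate, confined to new subjects, and that subjects ADA-positive at Day 1 are rollovers. Take the maximum of 250 subjects with about 40 new (Section 3.1), leaving 210 rollovers. Assume 0.1 per year in rollovers, 0.2 or 0.5 per year in new subjects during months 0 to 3, and no ADA effect. The positive group's rate is 0.1. The negative group's rate in months 0 to 3 is:

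- 10% of rollovers positive (189 rollovers and 40 new are negative): (18.9 + 8)/229 = 0.117, ratio 0.85; or (18.9 + 20)/229 = 0.170, ratio 0.59.
- 30% positive (147 and 40 are negative): (14.7 + 8)/187 = 0.121, ratio 0.82; or (14.7 + 20)/187 = 0.186, ratio 0.54.

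ADA would look protective (0.54 to 0.85) although it has no effect. Splitting by time interval alone is therefore not enough for the ADA summary. The two sources of subjects must also be shown apart.

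**The case against.** **Section 8 defers detail.** Section 8.1 says: "This section presents a brief summary of the planned statistical analyses". The full analysis is left to a SAP that is not in the file, the quoted n (%) rule is a general one, and incidence in Section 8.5 does not exclude a rate. All of this stands. A reader might infer that the sponsor has decided against exposure-adjusted rates. The documents do not support that; they show only that the stated text does not provide them.

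**The planned comparisons may be little affected.** There is one treatment and no test. Cohorts are defined by oral estrogen use, and nothing suggests that follow-up differs by estrogen use. One can construct a large ratio: with λ = 0.10, one group followed for 2 to 3 years and another for 0.5 to 1.5 years show 22.1% and 9.5%, a ratio of 2.33. A reader might take this as the bias in the cohort tables. It is not, because the plan makes no comparison between groups with those follow-up times. What remains is the difficulty of reading any single percentage.

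**Person-year rates have their own weakness.** If the hazard is higher early, the overall rate also depends on follow-up. With an assumed 0.3 per year for 3 months and 0.1 afterwards, expected events per person-year are (0.075 + 0.025)/0.5 = 0.20 at 6 months and (0.075 + 0.275)/3 = 0.117 at 3 years. This stands, and it is why interval incidence belongs beside the overall rate.

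**ADA.** A reader might infer that the ADA summary is biased upward, because longer follow-up gives more chance both to convert and to report an AE. That needs an ever-positive rule, which no section states, plus conversion spread over time and widely varying follow-up. The only timing documented is paediatric (Section 1.1.2: first seen at Month 3, then consistent). In a simulation with no true effect, 30% converting at Month 3 and nobody leaving earlier, the crude ratio was 0.99 to 1.01. Adult timing is unknown, so the supportable point is only that the rule is missing.

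**Conclusion.** The point holds as a gap in the stated text. Read as written, the primary safety result is a crude percentage over unequal, open-ended follow-up, with no link to time observed. The conclusion rests on unequal follow-up, which follows from sequential entry and an end date that can differ by country. It does not depend on any assumed rate. The size in this trial cannot be given. The spread from 4.9% to 25.9% at 0.10 per person-year is an illustration under a constant hazard. No error rate or treatment contrast is affected, and the separate SAP may already cover the matter. The ADA timing question is secondary. This is a cheap improvement, not a flaw that undermines the study.

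**What to change.** In Section 8.5 or the SAP, keep n (%) and make these additions.

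- **Rates.** By cohort, overall, and split by rollover versus somavaratan-naive subjects, report first events per 100 person-years to first event, and all events per 100 person-years, with descriptive 95% intervals. Do this for TEAEs, related TEAEs, SAEs and Grade 3 or higher events. For all-event rates, the interval should allow for repeated events within a subject.
- **Interval incidence.** Report AE incidence by time since first dose in this study (for example 0–3, 3–6, 6–12, 12–24 and over 24 months), with the number at risk.
- **Time at risk.** Define its start and end. State whether the roughly 60 days of post-dose follow-up (Section 6.1.8) count, and whether time on once-monthly dosing in this study before the switch (Sections 3.1 and 4.2) counts.
- **ADA.** State when status is assigned and how a later negative sample is handled. If AEs are compared by ADA status, do so within time intervals or from a landmark such as Month 3, and separately for rollover and naive subjects. Present this as descriptive; it is not guaranteed free of bias.

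The cost is SAP wording, two added tables and a revised ADA table, from dates already collected. Overall rates assume a roughly constant hazard, which the interval table lets readers check. Cells will be small in the ADA and naive-subject splits. A landmark counts later converters as negative, which dilutes any real effect. ADA sampling every 3 and then 6 months limits how closely conversion can be dated.

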3 INVESTIGATIONAL PLAN

3.1 Overall Study Design and Plan

This open-label extension study will evaluate the safety of long-term twice-monthly administration of somavaratan in adults with GHD. This study is open to subjects completing a Versartis adult GHD study as well as approximately 40 new somavaratan naïve subjects (either rhGH treatment naïve or currently receiving daily rhGH therapy). A total of up to 250 subjects may be enrolled in this study. All subjects will receive twice-monthly (every 15 days \pm 2 days) subcutaneous (SC) somavaratan. All subjects will have somavaratan doses titrated per the Dose Titration Plan (Table 2) to each subject's individual IGF-I responses based on the IGF-I level collected 7 days post-dose (Day 8) until a maintenance dose is achieved. Maintenance dose is defined as an IGF-I value between 0 and 2.0 SDS for two consecutive 7 day post-dose time points (peak).

Subjects receiving somavaratan once-monthly in this study (Protocol 15VR8) or in a previous somavaratan study (Protocol 15VR7), will have their dose decreased by half (minimum dose of 20 mg, 40 mg for women on estrogen, rounded down the nearest even number) and will be titrated per the Dose Titration Plan (Table 2).

New subjects naïve to somavaratan treatment enrolling in this study will be assigned to one of two cohorts and will receive a starting dose of 20 mg twice-monthly (40 mg for women on estrogen) (Table 1) and will be titrated per the Dose Titration Plan (Table 2).

Maintenance doses may be adjusted further at the discretion of the Investigator or Medical Monitor while maintaining IGF-I at Day 8 (7 days post dose) within target range. For patients on maintenance dose that have IGF-I levels $>$ 2.0 SDS at any point during the maintenance period, dose adjustment shall be made by the Investigator or Medical Monitor based on clinical judgment with the objective to achieve and maintain IGF-I at day 7 post-dose between 0 and 2.0 SDS. Any change in somavaratan dose in a subject that has achieved maintenance dosing will be followed by an ad-hoc Day 8 IGF-I measurement to ensure IGF-I values are within target range (0 and 2.0 SDS).

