Study visits/blood sample collections will occur every week during the first month of the study, followed by monthly clinic visits until the subject has reached maintenance dose. Once maintenance dose is achieved, in clinic visits will occur quarterly during the first year. Although quarterly visits will continue throughout the study, after the first year blood samples will be collected every 6 months, with intervening visits used for brief physical exams and collection of AEs and concomitant medications.

In current clinical practice with daily rhGH products, individualized dose titration is the standard of care. Daily rhGH doses are titrated to achieve normalization of IGF-I (the primary PD parameter) without jeopardizing safety. Each patient may have different IGF-I and safety

responses to daily rhGH treatment, especially with regards to potential adverse events such as edema. The IGF-I response to rhGH depends on many factors. One of the mostly recognized is the exposure to estrogens, in particular oral estrogens, which confers relative resistance to rhGH. Consequently, subjects will be stratified into the following two cohorts:

- Cohort 1: adults with GHD irrespective of age and gender will receive a starting dose of 20 mg twice-monthly
- Cohort 2: women receiving oral estrogen will receive a starting dose of 40 mg twice-monthly

Subjects entering the study currently receiving daily rhGH treatment must have discontinued rhGH for a minimum of 14 days prior to initiating treatment with somavaratan. Additionally, these subjects must have a baseline IGF-I SDS ≤ 0 .

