8.3 Demographics and Baseline Characteristics

Demographic and Baseline characteristics (including age, gender, race, weight, height, BMI, Baseline IGF-I level and IGF-I SDS) will be summarized by cohort and for the overall population using descriptive statistics.

Medical history and clinical laboratory tests results will be listed.

Prior and concomitant medications will be summarized by cohort and by the number and percentage of subjects taking each medication.

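### One Baseline rule, different starting points: laboratory and vital-sign change tables and laboratory shift tables are not split by prior somavaratan exposure

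*Combined protocol and SAP*

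**What the plan says.** Section 8.1 of the protocol defines Baseline once, for all subjects: "The last observation obtained prior to the first dose in the current study will be used as the Baseline value". It also says: "All summaries will be presented by cohort".

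Section 8.5 then plans two kinds of table on that Baseline. For laboratory panels and vital signs: "Observed and change from Baseline values for laboratory safety panels and vital signs will be summarized using descriptive statistics". For laboratory results in addition: "Laboratory results will also be summarized and presented as shifts from Baseline". Both are on the safety population, by cohort.

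Cohort is defined in section 3.1: "Consequently, subjects will be stratified into the following two cohorts". Cohort 2 is women receiving oral estrogen and Cohort 1 is other adults with GHD. Prior somavaratan exposure plays no part. Demographic and Baseline data (section 8.3) "will be summarized by cohort and for the overall population using descriptive statistics", which adds a total column but no exposure split. The only other split in the text is by anti-drug antibody status (Synopsis, Statistical Methods), for AEs, PK and PD.

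The study enrols people with different histories. Section 3.1 admits completers of the sponsor's earlier adult GHD studies and about 40 somavaratan-naive subjects. It also says: "Subjects receiving somavaratan once-monthly in this study (Protocol 15VR8) or in a previous somavaratan study (Protocol 15VR7), will have their dose decreased by half". So some subjects had once-monthly doses in 15VR7 and some had them within 15VR8 itself.

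**The concern.** The primary objective is long-term safety and the study is descriptive, so the tables are the result. A mean change or a shift count is easy to read only if the subjects in a column start from a comparable point. Here a column could combine change since first exposure to the drug with change since entry to an extension after months of treatment. If a laboratory value moved during 15VR7 and then stayed where it was, the extension tables would show that subject as unchanged.

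The measures where this could matter are those that may move slowly or that have already been linked to the drug. Section 5.7.5 lists increased cholesterol (LDL, triglycerides) and increased lymphocytes among the events reported as related in adults, and both lipids and the white-cell differential are in the planned panels (Table 3).

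**Working it through.** The plan states no sample size, power or effect figure for these tables, so there is nothing to reproduce. The check sets the Baseline rule against the entry rules.

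**Step 1. What Baseline represents, by route of entry.**

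| Route of entry | What precedes Baseline | What change from Baseline measures |
|---|---|---|
| New subject (sections 3.1, 3.6) | No somavaratan; some are at least 14 days off daily rhGH | Change since first somavaratan |
| Rollover from once-monthly dosing in 15VR7 (sections 4.2, 5, 6.1.2) | Once-monthly somavaratan, with no washout specified | Change since entry to the extension |
| Already dosed once monthly inside 15VR8 (sections 3.1, 4.2) | Whatever preceded the first 15VR8 dose, which was a once-monthly dose | Change across the once-monthly and the twice-monthly regimens |

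The second row rests on three provisions. Day 1 may coincide with the last visit of the previous study (section 5). End of Study assessments from that study may be used for entry if no more than 30 days old (section 6.1.2). Rollovers move to half of a dose they are currently receiving (section 4.2). The washout in section 3.7 concerns daily rhGH only. The amendment rationale reports 29 subjects who had completed five doses in the Phase 2 study, so pre-Baseline exposure for such subjects is five doses, against none for new subjects. The second and third rows can overlap: a subject may have come from 15VR7 and then had once-monthly doses in 15VR8.

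**Step 2. Whether the tables combine these routes.** The text points both ways.

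- For pooling: section 3.1 stratifies subjects without limiting the statement to new ones. It titrates everyone by Table 2, whose columns are the two cohorts. Section 4.2 mentions a cohort assignment for subjects already on once-monthly dosing.
- Against: the Synopsis, section 3.1 and section 4.2 each explicitly assign only new subjects to the two cohorts, and section 8 does not say where rollovers fall.

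Pooling is the better reading, because a rollover cannot be titrated by Table 2 without a cohort and all summaries are by cohort. If it is the wrong reading, the plan does not say in which column rollovers are summarised, and that also needs a sentence.

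**Step 3. What the tables would show.** Take two subjects in one cohort whose LDL is normal before any somavaratan, rises above range in the first months of treatment and stays there. The new subject is counted as a shift from normal to high, with a positive change. The 15VR7 rollover whose rise occurred in the parent study is counted as high to high, with a change near zero. The rollover's high level is visible in the Baseline category and in the observed-value summary, but not as change or shift.

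**Step 4. Size.** Two inputs are needed: the share of rollovers in each cohort, and the share of a rollover's total change that occurred before 15VR8. The documents give neither. The nearest evidence is in the amendment rationale: trough IGF-I in 15VR7 was similar to pre-exposure values, and by 21 days after the fifth dose IGF-I was no different from pre-dose. That suggests little carry-over for trough IGF-I. It does not address lipids, HbA1c, glucose, other safety laboratory tests or vital signs.

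**The case against.** An extension baseline is an ordinary and legitimate choice, and change since extension entry is a uniform definition. That stands: the point concerns how the tables are split, not the Baseline rule itself.

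Section 8.1 calls itself a brief summary and leaves details to a separate SAP, which is not among the documents. Section 9.10 would have that SAP final before enrolment, modifiable until database lock, and subjects had already rolled over by the amendment. An SAP with the split may therefore exist. This cannot be checked, and nothing in the supplied text plans the split.

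The practical harm is small. Section 8.5 also summarises observed values, the Synopsis lists safety data by subject, adverse-event summaries do not use the change score, and no hypothesis is tested. Exclusion criterion 7 keeps out subjects with a historical or Screening FPG or HbA1c above its limits, which restricts the larger glucose shifts that could be missed. All of this stands and sets the grade of the point.

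A reader might infer more than the documents support, in three ways.

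- That every subject from an earlier study is on drug at Baseline. Section 3.1 admits completers of any of the sponsor's adult GHD studies, and section 1.1.1 describes a single-dose study that included placebo subjects.
- That the dilution can be computed, for example from 29/(29 + 40) = 42% rollovers. That ratio mixes a count of completers at the amendment date with a recruitment target, assumes all 29 rolled over, and is not a cohort share. Even a correct share would not give the dilution without the second unknown in Step 4.
- That a safety signal is being hidden. The documents report no laboratory or vital-sign drift in 15VR7, and levels remain visible in the observed data.

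**Conclusion.** The point holds as a cheap improvement. Under the stated rules, Baseline falls during ongoing treatment for subjects rolling over from once-monthly dosing in 15VR7, before any somavaratan for new subjects, and before a different regimen for subjects dosed once monthly inside 15VR8. The planned laboratory and vital-sign change tables and laboratory shift tables do not separate these groups. A change that began in 15VR7 would show as a Baseline level.

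The conclusion assumes that rollovers are placed in the two cohorts for the tables, which is the better reading but is not stated outright, and that no unseen SAP already adds the split. The size of the effect cannot be derived and could be nil for measures that return to pre-exposure values between doses.

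**What to change.** In section 8.5 or the SAP:

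- Present laboratory and vital-sign change tables and laboratory shift tables separately for subjects with and without somavaratan exposure before their first 15VR8 dose, in addition to by cohort.
- State how a rollover's cohort is set for the tables.
- Flag subjects who had once-monthly doses inside 15VR8, whose change covers both regimens.

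In section 8.1, keep the current value and label it the extension baseline.

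Optionally, add a supplementary baseline for rollovers, taken before their first somavaratan dose, for measures that 15VR7 also collected. It should be labelled as spanning both regimens. The 15VR7 protocol is not among the documents, so which measures qualify would have to be confirmed.

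The required changes are a few lines and need no new data. The costs are extra tables and small cells in the oral-estrogen cohort. The optional baseline would also need a merge with parent-study data.
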